Prior/concomitant therapy

- E 11. Medical condition requiring concomitant administration of a medication with a narrow therapeutic window, that is metabolized by cytochrome P450 (CYP450) (see Appendix 11 [Section 10.11]), and for which a dose reduction cannot be considered.
- E 12. Medical conditions requiring concomitant administration of strong CYP3A inhibitor (see Appendix 11 [Section 10.11]), unless it can be discontinued at least 2 weeks before the first administration of study intervention.
- E 13. Concurrent treatment with any other anticancer therapy.
- E 14. Washout period before the first administration of study intervention of less than 3 weeks or less than 5 times the half-life, whichever is shorter, for prior anti-tumor therapy (chemotherapy, targeted agents, immunotherapy and radiotherapy, or any investigational treatment), if palliative radiotherapy washout period of less than 2 weeks.
- E 15. Any prior therapy targeting CEACAM5.
- E 16. Prior maytansinoid treatment (DM1 or DM4 anti-body drug conjugate [ADC]).

Prior/concurrent clinical study experience

E 17. Previous enrollment in this study, current participation in any other clinical study involving an investigational study treatment, or any other type of medical research.

Diagnostic assessments

E 18. Poor organ function as defined by any 1 of the following prior to IMP administration:

- a) Serum creatinine >1.5 × upper limit of normal (ULN) or estimated glomerular filtration rate (eGFR) <60 mL/min/1.73 m² as estimated using a Modification of Diet in Renal Disease (MDRD) formula.
- b) Total bilirubin >1.0 × ULN (excluding congenital conjugation disorders [Gilberts], for whom total bilirubin ≤3.0 × ULN, with direct bilirubin ≤1.5 × ULN, is allowed). or aspartate aminotransferase (AST), alanine aminotransferase (ALT) >2.5 × ULN (in case of documented liver metastasis, AST, ALT <5 × ULN is allowed).

- c) Neutrophils $<1.5 \times 10^{9}$ /L, platelet count $<100 \times 10^{9}$ /L, or hemoglobin <9 g/dL (blood infusion-free for at least 2 weeks).

Other exclusions

- E 19. Individuals accommodated in an institution because of regulatory or legal order; prisoners or participants who are legally institutionalized
- E 20. Any country-related specific regulation that would prevent the participant from entering the study see Appendix 8 (Section 10.8) of the protocol (country-specific requirements)

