8.2.6.6 Liver function tests

- Hepatic enzyme increase has been reported with tusamitamab ravtansine administration. Patients should be carefully followed and in case of Grade ≥3 abnormal liver function tests, additional liver function tests will be done every 2 to 3 days until recovery to baseline value. Tusamitamab ravtansine should be permanently discontinued in case of drug-induced Grade 4 liver enzyme increase.
- Grade \geq 3 (ie, >5 × ULN) increased liver enzyme events should be reported as AESIs.

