For laboratory variables, analyses according to NCI grading will be made based on NCI-CTCAE version 5.0. In addition, for laboratory variables for which NCI-CTCAE scale is not applicable, vital signs and ECG variables, PCSA analyses will be performed based on the PCSA list currently in effect at Sanofi at the time of the database lock.

Analyses according to PCSA and NCI grading will be performed based on the worst value during the treatment-emergent period, using all measurements (either local or central, either scheduled, nonscheduled or repeated).

QTcF prolongation will be graded according to NCI-CTCAE version 5.0. The frequency of participants in each grade of QTcF prolongation during the on-treatment period will be summarized. For participants with multiple occurrences of QTcF prolongation during the treatment, the maximum grade by participant will be used.

For laboratory variables, vital signs and ECG variables, the incidence of participants with at least one PCSA during the treatment-emergent period will be summarized regardless of the baseline level and according to the following baseline status categories:

- Normal/missing.
- Abnormal according to PCSA criterion or criteria.

The number (%) of participants with QTcF abnormality worsening during the on-treatment period (worst value per participant) according to baseline value will be displayed.

For laboratory variables graded by NCI-CTCAE version 5.0.

- The number (%) of participants with abnormal laboratory tests at baseline will be presented by grade.
- The number (%) of participants with abnormal laboratory tests during the treatment-emergent period will be summarized by grade. When appropriate, the number (%) of participants with abnormality of any grade and with Grade 3-4 abnormalities will be provided.

For laboratory variables not graded by NCI-CTCAE nor by PCSA, the number (%) of participants with laboratory test outside normal ranges will be provided.

Additional analyses for drug-induced liver injury

The following additional analyses will be performed for drug-induced liver injury:

- For each liver function test (eg, ALT), participants having experienced a PCSA will be summarized considering worst on-treatment value.
- A graph of the distribution of peak values of ALT and AST versus peak values of total bilirubin during the treatment-emergent period will be provided.

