- For each liver function test (eg, ALT), participants having experienced a PCSA (eg, ALT >5 ULN) will be summarized using the following categories: Returned to baseline PCSA status (or returned to value ≤ ULN in case of missing baseline) before last IMP dose, Returned to baseline PCSA status after last IMP dose, Never returned to baseline PCSA status, No assessment after elevation. This summary will be performed by categories of elevation (ALT >3, >5, >10, >20 ULN).
- A listing of possible Hy's law cases identified (eg, participants with any elevated AST or ALT of >3 ULN and elevated Total bilirubin >2 ULN, 2 days apart), will be provided, displaying ALT, AST, Total bilirubin and ALP values.

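### The liver-test recovery table can count a participant as returned with no fall if baseline was already above the row's threshold, and it handles missing baselines inconsistently

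*SAP*

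**What the plan says.** In SAP 3.6.3.1, the additional analyses for drug-induced liver injury take, for each liver function test, "participants having experienced a PCSA (eg, ALT >5 ULN"), and sort them by outcome. The first category is "Returned to baseline PCSA status (or returned to value ≤ ULN in case of missing baseline) before last IMP dose". The others are "Returned to baseline PCSA status after last IMP dose, Never returned to baseline PCSA status, No assessment after elevation". On the rows, the SAP says: "This summary will be performed by categories of elevation (ALT >3, >5, >10, >20 ULN").

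The only levels of baseline PCSA status written in the SAP appear earlier in the same section, for the incidence summaries. There are two: "Normal/missing" and "Abnormal according to PCSA criterion or criteria". The PCSA criteria come from a sponsor list in force at database lock, which neither document reproduces.

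Protocol 5.2, E 18b, excludes ALT or AST above 2.5 × ULN, with one exception: "in case of documented liver metastasis, AST, ALT <5 × ULN is allowed". It sets no limit for ALP. For Grade 3 or higher abnormal liver tests, Protocol 8.2.6.6 says "additional liver function tests will be done every 2 to 3 days until recovery to baseline value".

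**The concern.** A status has few levels and a laboratory value has many. If a participant starts in the abnormal status, staying there satisfies a rule that asks only for the baseline status, whatever the enzyme has done. The rule then records recovery where none took place.

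This table is the SAP's planned summary of whether liver-test elevations reverse. Hepatotoxicity is a listed risk (Protocol 2.3.1, Table 1), Grade 3 or higher liver enzyme increase is an adverse event of special interest (Protocol 8.3.7), and there is no control arm. A count that includes automatic returns overstates reversibility.

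The second difficulty is that a missing baseline gets its own, stricter standard in one outcome category, while the incidence summaries in the same section treat missing as normal.

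**Working it through.** The plan gives no figure to reproduce. The check applies the rule as written to each elevation row.

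**Inputs.** Rows T = 3, 5, 10 and 20 × ULN (SAP 3.6.3.1). The SAP names ALT for these rows; I apply them to AST as well, since the summary covers each liver function test. Entry limits are from E 18b. I assume the baseline value, which SAP 3.1 defines as the last before first dose, itself meets E 18b.

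**Rule.** A participant is in row T if the peak exceeds T.
- Two-level status per row: returned if the last value is on the same side of T as baseline.
- Banded status (≤3, >3 to 5, >5 to 10, >10 to 20, >20): returned if the last value is in the baseline band.
- Missing baseline: returned if the last value is ≤1 × ULN.

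**Who can enter above a row.** Without liver metastasis the highest eligible ALT or AST is 2.5 × ULN, which is above no row. With liver metastasis it is below 5 × ULN, which is above the >3 row only.

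**Worked cases (multiples of ULN).**

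| Baseline | Peak | Last | >3 row | >5 row | >10 row | Banded status |
|---|---|---|---|---|---|---|
| 4.0 | 4.8 | 4.8 | returned | not in row | not in row | returned |
| 4.9 | 6 | 6 | returned | not returned | not in row | not returned |
| 4.0 | 12 | 12 | returned | not returned | not returned | not returned |
| 1.0 | 6 | 2.9 | returned | returned | not in row | returned |
| missing | 6 | 2.9 | not returned | not returned | not in row | not applicable |

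The row columns use two-level status. In the first case the participant is returned with no fall under both readings. In the second and third the value has risen and stayed up; the >3 row still says returned under two-level status, but the higher rows show no return.

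**Missing baseline.** With a normal baseline the ceiling for returned is T; with a missing baseline it is 1 × ULN. The ratio is T/1: 3, 5, 10 and 20 for the four rows, and 5 for the SAP's own example of ALT >5 × ULN. It would be 3 in every row only if status meant not exceeding the lowest criterion, 3 × ULN. The last two cases show the same course classified differently. The ≤ULN rule is written only for return before the last dose, so a later return with a missing baseline has no stated standard.

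**ALP.** E 18b gives no ceiling and the documents give no cut-off, so the affected range cannot be calculated.

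**The case against.** The strongest reply is that the SAP does not expressly count these participants as returned. It leaves the abnormal-baseline case undefined, the criteria sit in a list we cannot see, and a banded status would remove the worst cases. It could add that a true rise is caught in the next row up, that missing baselines should be very rare, and that the table is descriptive. Missing baselines should be rare because laboratory tests are due within 7 days before dosing (Protocol 1.3.1), E 18b needs ALT and AST, and waivers are barred.

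Much of this stands. It limits the scope and lowers the severity. It does not remove the defect: a banded status is written nowhere, and even under it a participant who goes from 4.0 to 4.8 × ULN and stays there is returned.

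A reader might infer four stronger points, which the documents do not support.
- *That the table is unsound in every row.* For ALT and AST the no-fall case is confined to the >3 row.
- *That one misclassification moves the recovery share by 30 to 40 percentage points.* That comes from Grade 3 or higher laboratory rates in Protocol Table 1: AST 12 of about 184, or 6.5%, × 38 = 2.5; ALP 15 of about 183, or 8.2%, × 38 = 3.1; 1/3.1 to 1/2.5 is 32% to 40%. Protocol 8.2.6.6 equates Grade 3 or higher with more than 5 × ULN, where the ALT/AST error cannot occur. The >3 row is at least as large and its size is not given; the ALP figure needs the unseen cut-off.
- *That the SAP contradicts a protocol definition of recovery.* Protocol 8.2.6.6 says how long to repeat tests. Section 8.2.5 also accepts normal values or values no longer clinically significant, and Table 10 uses Grade 1 for restarting treatment. None defines an analysis.
- *That counting a fall below a labelled threshold from a normal baseline is an error.* That is a reporting choice, and the row label discloses it.

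**Conclusion.** The point holds in a narrow form and is minor. As written, the rule can report recovery without any fall for participants already above a row's threshold at baseline. For ALT and AST that means the >3 row only, with liver metastasis and a baseline above 3 and below 5 × ULN. If status is two-level, a rise also counts as returned in that row, although the >5 row shows it as not returned once the value exceeds 5 × ULN. The same can occur for ALP, to an extent that cannot be computed. The number of participants entering in these ranges is not given, so no percentage effect can be stated.

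The missing-baseline rule is 3 to 20 times stricter by row if status is judged row by row. It is out of line with the pooling of missing and normal in the same section and incomplete across outcome categories, but it should seldom be used.

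The consequence is confined to one descriptive safety table. ORR, the interim rule and the sample size are unaffected. Other planned outputs, such as grade at baseline and worst grade, the peak ALT/AST against bilirubin plot and the listing of possible Hy's law cases, would still show the underlying elevations.

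**What to change.** Amend SAP 3.6.3.1 in four places.

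1. Restrict each elevation row to participants whose baseline was at or below that row's threshold.
2. List those already above it separately, by test, with baseline, peak and last values.
3. State whether status is judged against each row's own threshold or by bands, and give the cut-offs for tests other than ALT, ALP in particular.
4. Apply one missing-baseline rule to every outcome category, in line with the incidence summaries. The simplest is to treat missing as normal in both places. If the ≤ULN standard is kept, write it for return before and after the last dose and for never returned, and change or explain the pooling.

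This needs no new data and no change to conduct. The cost is SAP wording, slightly more programming and one short listing. The rows may hold fewer participants, and the recovery share may look less favourable.

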3.6.3.2 Ocular examinations

Schirmer test

Participants reported Schirmer's test will be classified into three classes at baseline: normal ≥ 10 mm, moderate >5 and <10 mm, severe ≤ 5 mm (8). The worst classification between the laterality will be considered. A frequency table of the baseline status with and without anaesthetics will be provided by treatment group for the participants with corneal events (CMQ) during the treatment-emergent period and for the participants without event.

Visual acuity test

Analyses are done on the best corrected visual acuity assessed using Snellen Chart method.

Frequency tables on best corrected visual acuity (BCVA) measured during on-treatment period will be performed separately on all participants and on participants who experienced at least one treatment-emergent corneal event:

- on the worst change from baseline: No worsening versus baseline, Worsening versus baseline (1 to 3 lines decrease versus baseline, or >3 lines decrease versus baseline)
- on the worst absolute value: No change versus baseline, Worsening versus baseline: BCVA equals to 20/40 or better, BCVA worse than 20/40 up to 20/200, BCVA 20/200 or worse.

- on the CTCAE worst vision decrease: No worsening versus baseline, BCVA equals to 20/40 or better or 1 to 3 lines decrease versus baseline, BCVA worse than 20/40 up to 20/200 or >3 lines decrease versus baseline, BCVA 20/200 or worse.
- For participants who had worsening versus baseline on BCVA, the outcome on the last BCVA value will be displayed: Recovered to baseline, Not recovered to baseline, Lost to follow-up or dead with ongoing corneal events

A participant will be considered as lost to follow-up if the participant discontinued the study and did not perform any follow-up visit.

A shift table of the category of the last BCVA value (Normal (20/20 or better), worse than 20/20 up to 20/40, worse than 20/40 up to 20/200 or 20/200 or worse) versus the category of the worst BCVA value (20/40 or better, worse than 20/40 up to 20/200, 20/200 or worse) will be performed for participants who experienced at least one treatment-emergent corneal event.

For the summary table on participants who experienced at least one treatment-emergent corneal event, the worst value and the worst change from baseline are measured during any of the treatment-emergent corneal events experienced by the participant (between start date and end date of the corneal events). For the summary table on all participants, all on-treatment BCVA values are considered.

The worst classification between the laterality will be considered for the worst value of participant either left or right eye then the change from baseline and the last value will be measured from same eye with worst value. If the worst absolute value is the same for both eyes, then the eye with the worst change from baseline is considered, and if identical, then the eye with the worst last value is considered.

Participants whose baseline visual acuity had been reported in naked eye instead of BCVA (ie, whenever baseline value was worse than the values reported during the during the treatment period/treatment-emergent corneal events) will be excluded from this analysis.

Slit lamp examination

Descriptive statistics of slit lamp examination will be provided separately at baseline and at the time of first abnormal slit lamp after occurrence of a treatment-emergent corneal event and at the time of the worst BCVA value during a treatment-emergent corneal event for participants experiencing treatment-emergent corneal events (CMQ). The outcome (normal, abnormal), and for abnormal findings, the type of lesions and the distribution will be described by laterality (unilateral, bilateral, all).

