5.2 EXCLUSION CRITERIA

Participants are excluded from the study if any of the following criteria apply:

Medical conditions

- E 01. Untreated brain metastases that may be considered active or history of leptomeningeal disease. Patients with previously treated brain metastases may participate provided they are stable (ie, without evidence of progression by imaging for at least 4 weeks prior to the first administration of study intervention, and any neurologic symptoms have returned to baseline), and there is no evidence of new or enlarging brain metastases, and the patient does not require any systemic corticosteroids for management of brain metastases within 4 weeks prior to the first dose of study intervention.
- E 02. Life expectancy less than 3 months.
- E 03. Significant concomitant illness, including any severe medical condition that, in the opinion of the Investigator or Sponsor, would impair the participant's participation in the study or interpretation of the results.
- E 04. History within the last 3 years of an invasive malignancy other than the one treated in this study, with the exception of resected/ablated basal or squamous-cell carcinoma of the skin or carcinoma in situ of the cervix, or other local tumors considered cured by local treatment.
- E 05. Any major surgery within 3 weeks prior to Day 1 of first study intervention administration.
- E 06. Known uncontrolled infection with human immunodeficiency virus (HIV). Participants with well controlled HIV infection/disease (Section 10.10) must be on antiretroviral therapy (ART) to be eligible.
- E 07. Active infection with hepatitis A, B (defined as either positive HBs antigen or positive hepatitis B viral DNA test above the lower limit of detection of the assay), or C (defined as known positive result for antibodies to hepatitis C and known quantitative hepatitis C virus [HCV] RNA results greater than the lower limit of detection of the assay).
- E 08. Nonresolution of any prior treatment-related toxicity to <Grade 2 according to NCI CTCAE v5.0, with the exception of alopecia, vitiligo, or active thyroiditis controlled with hormone replacement therapy (HRT).

- E 09. Unresolved corneal disorder or any previous corneal disorder considered by an ophthalmologist to predict higher risk of drug-induced keratopathy.
- E 10. Use of contact lenses that the participant is unwilling to stop for the duration of the study intervention. The use of contact lenses is not permitted.

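### The rule that picks one eye by worst acuity lets the tables of worst vision change miss a participant's actual worst change

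*SAP*

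**What the plan says.** The visual acuity part of SAP section 3.6.3.2 plans frequency tables of on-treatment BCVA, for all participants and for those with a corneal event. One table is "on the worst change from baseline: No worsening versus baseline, Worsening versus baseline", with loss split into 1 to 3 lines and more than 3 lines. A second is on the worst absolute value, and a third on the worst vision decrease in CTCAE categories. A recovery display follows: "For participants who had worsening versus baseline on BCVA, the outcome on the last BCVA value will be displayed". A shift table sets the last BCVA category against the worst, for participants with a corneal event.

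One selection rule serves all of these. It opens "The worst classification between the laterality will be considered for the worst value of participant either left or right eye" and continues "then the change from baseline and the last value will be measured from same eye with worst value". The other eye comes in only on a tie: "If the worst absolute value is the same for both eyes, then the eye with the worst change from baseline is considered". The sentence "For the summary table on all participants, all on-treatment BCVA values are considered" settles which measurements enter, not which eye. No per-eye or any-eye BCVA change analysis is planned.

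On entry, Protocol section 5.2 (E 09) excludes "Unresolved corneal disorder or any previous corneal disorder considered by an ophthalmologist to predict higher risk of drug-induced keratopathy". It sets no minimum acuity and no limit on a difference between the eyes.

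**The concern.** The change and CTCAE tables are named for the participant's worst change, but the rule feeds them the change in the eye with the worst acuity. These are different quantities when the eyes start unequal. A participant may enter with one eye already poor from a non-corneal cause. If that eye stays as it was and the good eye loses vision during a corneal event, the tables follow the eye in which nothing happened.

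Protocol Table 10 grades keratopathy by acuity or by lines lost from known baseline, and at Grade 4 refers to the affected eye. Under the SAP rule the CTCAE-based table may describe the unaffected eye. A participant classed as not worsened also drops out of the recovery display.

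This matters because Protocol section 2.3.1 names corneal toxicity as the main anticipated risk and reports corneal events in 30.1% (56/186) at this dose in TED13751. The BCVA tables are the measured summary of its effect on vision.

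**Working it through.** The documents give no vision-loss rate and no share of participants with unequal eyes, so there is no planned figure to reproduce. The check applies the rule to possible eye pairs.

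**Inputs.** The selection rule and tie-break are from SAP 3.6.3.2. The acuity bands are 20/40 or better, worse than 20/40 up to 20/200, and 20/200 or worse. The Snellen steps are assumed, since the SAP lists none: 20/20, 25, 30, 40, 50, 60, 80, 100, 125, 160, 200, 250, 320, 400 (14 steps).

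**Two readings.** The closing words of the rule point to comparing eyes by raw value. The opening word, classification, also allows comparing them by band, which gives more ties. The bands overlap at exactly 20/200; it is put in the worst band here unless stated.

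**Worked pairs** (poor eye stable; lines counted on the assumed scale)

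| Poor eye | Better eye | Lines lost | Raw value | Band |
|---|---|---|---|---|
| 20/200 | 20/20 to 20/100 | 7 | 0, no worsening | 0, no worsening |
| 20/80 | 20/20 to 20/60 | 5 | 0, no worsening | 5, counted (tie) |
| 20/100 | 20/20 to 20/125 | 8 | 8, counted | 8, counted |
| 20/50 | 20/20 to 20/50 | 4 | 4, counted (tie) | 4, counted |

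If 20/200 is put in the middle band, the first pair ties under the band reading and is counted. With the poor eye at 20/250 it is masked under either placement.

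**All patterns with a stable poor eye and at least 1 line lost in the better eye.** The total is 1² + 2² + ... + 13² = 819.
- Raw value: masked when the better eye ends strictly between its baseline and the poor eye, C(14,3) = 364 of 819. With more than 3 lines lost, 165 of 550.
- Band: 216 of 819, and 84 of 550 with more than 3 lines lost. With 20/200 in the middle band, 207 of 819 and 84 of 550.

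**All patterns with no improvement in either eye.** (14 × 15 / 2)² = 105² = 11,025. The reported change never exceeds the larger of the two eyes' changes. The change class is too mild in 1,718 (raw value) or 936 (band). With equal baseline acuity there is no understatement. These are counts of patterns, not patient frequencies.

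**Shift table.** It has no baseline column, so direction is not fixed.
- Poor eye stable at 20/200, better eye 20/20 to 20/100 and back to 20/20: the table shows worst and last both at 20/200 or worse. An old deficit looks like unrecovered loss.
- Raw-value reading, poor eye 20/40 to 20/100 (4 lines) and back, better eye 20/20 to 20/80 (6 lines) and not recovered: the table follows the first eye and shows recovery.

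**Size, under assumptions.** Suppose the any-eye worsening rate were as high as the corneal event rate: 38 × 0.301 = 11.4 participants. If a share m of them were masked, with m assumed to be 0 to 20%, the number missed is 11.4 × m, or 0 to 2.3, and a true 30.1% would be reported as 30.1% down to 30.1 × 0.8 = 24.1%. At a true 10%, the number missed is 38 × 0.10 × m, or 0 to 0.8.

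**The case against.** The wording is ambiguous. The Schirmer paragraph of the same section uses similar language, and there each result is put in a class and the worse class is taken. Read that way, a 20/80 and a 20/60 eye tie and the loss is counted. If the row for no change is itself treated as a class, a worsened eye always outranks a stable one, and none of the 819 patterns is masked. The ambiguity is real, and the 20/80 pair should not be presented as certain. But the last version fits poorly with text that speaks of the eye with the worst value and of equal absolute values, and it still gives too mild a change class in 504 of the 11,025 patterns. The band reading leaves masking in place.

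A reader might infer that the rule biases every BCVA output towards safety. The shift table shows otherwise.

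A reader might also infer that one or two of about 11 participants with corneal events would be hidden, moving that table by 10 to 20 percentage points. That treats every participant with unequal eyes as masked. Masking also needs the better eye to lose acuity and stay better than the poor one. Corneal events include asymptomatic Grade 1 lesions, and the Protocol describes those observed as mild to moderate.

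Finally, vision loss is captured elsewhere. Grade 3 or higher keratopathy is an event of special interest, corneal events are summarised by worst grade and outcome, ocular symptoms are reported, and slit-lamp findings are described by laterality. The secondary safety endpoint is adverse events and laboratory abnormalities, not a vision-loss rate. This limits the consequence; it does not correct the BCVA tables. Following one prespecified eye keeps each participant's values consistent, but that does not make the selected eye's change the worst change.

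**Conclusion.** The concern holds for the tables of worst change and CTCAE vision decrease. They can miss a participant's worst change when the eyes differ at baseline and the better eye loses lines without reaching the poor eye's level. In these tables the result is always equal to or milder than the worse of the two per-eye results, and a masked participant also leaves the recovery display. In the shift table the error can run either way.

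The size cannot be computed from the documents. Zero to about two of 38 participants rests on an assumed masked share of 0 to 20% and on using the earlier study's corneal event rate as an upper value for acuity loss. Zero is possible, though a single missed case could be a loss of more than 3 lines. The documents do not support saying that ocular toxicity would be lost from the trial's safety reporting. This is a correction worth making to descriptive safety tables, with no bearing on the primary endpoint.

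**What to change.** Replace the eye-selection sentences in SAP 3.6.3.2 as follows.

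1. Derive the change from baseline and the CTCAE vision category separately for each eye, and assign the participant the worse result in each table.
2. For the recovery display, take the last value from the eye with the worst change. For the shift table, take both the worst and the last value from that eye. If the changes tie, the SAP's existing final tie-break on the worse last value can be kept.
3. Use the worst-value eye only for the absolute-value table. State there whether eyes are compared by value or by category, and to which band exactly 20/200 belongs. That table may still show a stable poor eye as unchanged, so its title should say which eye it follows.

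The existing rule already needs values by eye, so no new data are required. The cost is a short SAP edit and minor programming. The reported vision-loss rate may become slightly less favourable, and different tables may follow different eyes for the same participant, which a footnote should state.
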